3.5.6 Data Analysis

A detailed statistical analysis plan will be developed and made available online before the data analysis begins.

3.6 Cost and cost-effectiveness study

Costs will be estimated from a societal perspective, including all costs incurred by institutions and communities ¹⁰. Costs will be calculated using a combination of accounting records and "ingredient" estimates using unit costs and input quantities ¹¹. An Activity-Based Costing (ABC) methodology will be used, allowing for the categorization and allocation of all program costs to their core activities. Financial costs as well as economic costs (in-kind donations, household expenditures, etc.) will be collected.

To obtain these data, program documentation and expenditure information will be reviewed, and key informant interviews and focus groups will be conducted with staff involved in program implementation. Another outcome of these interviews and focus groups will be an estimate of time allocation; staff time allocation will be used using the ABC method to allocate staff costs among activities. Focus groups will be conducted with households to gain an understanding of the direct and indirect costs they incur in participating in the program. The effect of plausible variation in household cost estimates from the focus groups will be assessed through sensitivity analysis.

The analysis will include both the total costs of the program and the incremental costs of additional activities in the intervention area. Cost-effectiveness ratios will be calculated based on program costs and outcomes. Incremental cost-effectiveness ratios will be calculated by dividing the incremental costs in the intervention area by the number of cases of acute malnutrition prevented in the intervention area compared to the control area. This ratio represents the incremental cost of achieving an additional positive outcome in the intervention zone compared to the control zone. Comparison with other similar published work will be considered where appropriate.

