3.4 Research Questions

Main Research Question :

- What is the impact of PASIM on the prevalence of wasting in young children?
- What is the impact of PASIM on the recovery rate of wasted children?
- What is the impact of PASIM on the occurrence of relapses after treatment and recovery from wasting?

Secondary Research Questions along the Continuum of Care :

- What is the impact of PASIM on the incidence of wasting in young children?
- What is the impact of PASIM on the wasting screening coverage in young children?
- What is the impact of PASIM on enrollment in a program for treating cases that test positive in young children?
- What is the impact of PASIM on nutritional status at enrollment in treatment in young children?
- What is the impact of PASIM on the duration, coverage, and adherence of/to the treatment of emaciation in young children?
- What is the impact of PASIM on the psycho-cognitive development of young children?
- What is the unit cost of PASIM per beneficiary child?
- If there is an impact of the intervention, how cost-effective is PASIM?
- Is the intervention well implemented, in terms of coverage, effectiveness, uptake, fidelity/rationality of implementation, and potential for sustainability?

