intervention group) and an average of 2 children per month for 7 months in the 50 smallest villages in the study area (i.e., the medium-sized villages in the Mongo Health District: equally 25 in the control group and 25 in the intervention group). The children will all leave the cohort in the same month: counting the month of inclusion, the children will be seen for a maximum of 9 months (for children included at the start of the study) and a minimum of 3 months (for children included during the 7th month). This will result in a total sample of 1,750 children (10,500 visits in total of which 1,750 inclusions and 8,750 follow-ups, see Table 1). With 15% dropout, the size of this study would provide sufficient power to detect a relative decrease of about 35% in the longitudinal prevalence of wasting and a relative decrease of about 28% in the incidence of wasting, with a power of 80% and a statistical significance of 5%, taking into account the cluster effect at the village level and the imbalance in cluster size.

In each of the 100 villages, **these children will be randomly selected from a randomly ordered list from a census of children aged 0-6 months (conducted by the survey team in the first month of the survey).** Their parents will be offered the opportunity to participate in the study during a home visit (see **Voluntary and Informed Participation Process and Consent Documentation described in Section 4**). Children whose parents refuse or who are not located will be replaced until a maximum of three new children have been included in a given month, or until the list of eligible children is exhausted. Inclusion will end when 21 children have been included in each of the 50 largest villages and at least 14 children have been included in each of the other 50 villages. Inclusion in the cohort will begin in April and continue until October 31, 2021.

The **criteria for inclusion of** children in the main cohort are:

- 6-6.9 months of age
- Child singleton
- The mother must live in the study area from the time of inclusion.
- The agreement of the mother or guardian

The exclusion criteria are :

- Congenital malformations that make anthropometric measurements impossible.
- Mother intends to leave the study area by December 2021.

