The **Relapse Prevention Cohort (#3)** will include [6-23] months old children discharged from the program and living in the 100 villages in the study area. Given the small size of most villages and the required sample size, we have calculated that we need to enroll 8 children in the 50 largest villages and 6 children in the 50 average villages and follow them every month for 6 months each. This will result in a total sample size of 700 children (4,900 visits in total, including 700 inclusions and 4,200 follow-ups). Such a sample size would provide sufficient power to detect a decrease of about 33% in the incidence of relapse.

All available children in each village who are discharged from PCIMA treatment (identified based on nutrition unit registers) will be invited to participate in the study

until the required sample size is reached for each village. **During the discharge visit, parents will be asked if they agree to have their contact (first name, last name, village, and if possible, telephone or location) forwarded to the survey team for an explanatory home visit. If they agree, participation in the study will be offered during a follow-up home visit (see process for voluntary and informed participation and documentation of consent described in Section 4).** In villages with more children than necessary, the study team will select children from a randomly selected list. Inclusion must be completed by June 30, 2021, to allow 6 months of observation before December 31, 2021.

The inclusion criteria for the relapse study are:

- Child has been successfully treated for wasting (moderate or severe) and has been discharged from the national treatment program within the last 30 days.
- The child is between 6 and 23 months of age at inclusion.
- The child is singleton.
- The mother must live in the study area from the time of inclusion.
- The agreement of the mother or guardian

The exclusion criteria are :

- Congenital malformations that make anthropometric measurements impossible.
- Mother intends to leave the study area by December 2021.

Table 1: Chronology of Inclusion in the Main and Relapse Cohorts and the Number of Children Followed Monthly

	April	May	June	July	August	September	October	November	December
Primary Cohort									
Month of inclusion 1 (n = 250)					n = 250				
Month of inclusion 2 (n = 250)					n = 500				
Month of inclusion 3 (n = 250)					n = 750				
Month of inclusion 4 (n = 250)					n = 1 000				

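### The cost-effectiveness ratio is planned with household-cost variation as its only uncertainty analysis; the sampling error in cases prevented is not carried into it

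*Protocol*

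**What the plan says.** Protocol section 3.6 takes a societal perspective and obtains the incremental ratio by dividing the added cost in the intervention area "by the number of cases of acute malnutrition prevented in the intervention area compared to the control area". It does not say which cohort or which outcome supplies those cases. The one uncertainty analysis it names concerns the numerator: "The effect of plausible variation in household cost estimates from the focus groups will be assessed through sensitivity analysis". The calculation carries no condition: "Cost-effectiveness ratios will be calculated based on program costs and outcomes".

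The research questions in protocol section 3.4 pose it differently: "If there is an impact of the intervention, how cost-effective is PASIM"? What counts as an impact is not defined.

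Elsewhere, protocol section 3.5.4 says only that a sub-study will evaluate cost-effectiveness, and section 3.5.6 leaves analysis detail to the SAP. The SAP has no cost-effectiveness section. Neither document mentions an interval, a bootstrap, a probabilistic analysis or an acceptability curve for the ratio.

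**The concern.** Cases prevented is an estimate, and it carries the full sampling error of a cluster trial with 50 villages per arm. A ratio divides by that estimate, so error in a small denominator is magnified. If section 3.6 is followed as written, the range around the ratio will show how it responds to household costs and nothing else. A reader could take that range as the uncertainty of the result.

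The audience makes this matter. Protocol section 3.8 sends the findings to programme planners, implementers, funders and decision-makers, for whom cost per case prevented is likely to be a prominent figure.

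The reporting rule is a second, smaller issue. Section 3.4 can be read as asking for the ratio only after a positive finding, whereas section 3.6 plans it in any event. A ratio shown only after a significant result rests on an effect selected for being large, so it would tend to look too cheap.

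**Working it through.** **Inputs.** Protocol section 3.5.3 gives three detectable effects:
- cohort 1 incidence: "a relative decrease of about 28% in the incidence of wasting, with a power of 80% and a statistical significance of 5" per cent;
- cohort 1 longitudinal prevalence: "a relative decrease of about 35% in the longitudinal prevalence of wasting", same power and significance;
- cohort 3: "sufficient power to detect a decrease of about 33% in the incidence of relapse". Power and significance are not restated there, so 80% and 5% are assumed.

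Tests are two-sided (SAP 6.1). Incidence and longitudinal prevalence are analysed by Poisson mixed models (SAP 6.4.1), so the natural scale is the log ratio.

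**Reproducing the plan's figures.** The cohort 1 counts reproduce: 50×3×7 + 50×2×7 = 1,750 children, and 250×(9+8+7+6+5+4+3) = 10,500 visits. The 28% cannot be re-derived, because neither baseline incidence nor the intra-cluster correlation is given for cohort 1. Its implications can be back-solved:
- SE of the log rate ratio = |ln 0.72| / (1.960 + 0.842) = 0.3285 / 2.802 = 0.117.
- With variance = DE × (1/E0 + 1/E1) and E1 = 0.72 × E0, control-arm cases are E0 = DE × (1 + 1/0.72) / 0.1173² ≈ 174 × DE.
- Follow-up per arm is 8,750/2 = 4,375 child-months, or 3,719 after 15% loss. That implies 4–5% per child-month at DE = 1 and 8–9% at DE = 2. DE is an assumption.

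**Range at the design effects, costs held fixed.** The 95% interval for the rate ratio is exp(−0.3285 ± 1.96 × 0.1173) = 0.572 to 0.906, so 9.4% to 42.8% of cases are prevented. With the control rate also held fixed, the ratio runs from 0.28/0.428 = 0.65 to 0.28/0.094 = 2.98 times its point estimate. The span is 0.428/0.094 ≈ 4.55-fold (unrounded inputs).

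| Basis | SE | Reduction, 95% interval | Span of the ratio |
|---|---|---|---|
| 28%, incidence, log scale | 0.117 | 9.4% to 42.8% | 4.55-fold |
| 35%, longitudinal prevalence, log scale | 0.154 | 12.1% to 51.9% | 4.28-fold |
| 33%, relapse, log scale | 0.143 | 11.3% to 49.4% | 4.36-fold |
| Any effect, difference scale | – | 0.30 to 1.70 times the estimate | (2.802+1.960)/(2.802−1.960) = 5.66-fold |

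**Range at other observed effects, same SE of 0.117.** The span is 7.2-fold at an observed 25%, 2.7-fold at 35% and 1.6-fold at 50%. The interval reaches no effect at 1 − exp(−1.96 × 0.1173) = 20.5%. At or below that observed reduction the ratio has no upper bound.

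**Size of the selection effect, if the ratio were shown only after a significant benefit.** Two million log rate ratios were drawn for each true effect, with SE 0.117, and kept when z < −1.96. The ratio was then compared with its true value.

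| True reduction | Chance of significance | Mean reduction when significant | Mean ratio / true | Median ratio / true |
|---|---|---|---|---|
| 35% | 0.96 | 35.4% | 1.03 | 0.99 |
| 28% | 0.80 | 30.6% | 0.95 | 0.93 |
| 20% | 0.48 | 27.3% | 0.755 | 0.758 |
| 15% | 0.28 | 26.0% | 0.59 | 0.60 |

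**The case against.** The strongest reply is that section 3.6 is a short outline of a sub-study and the SAP covers the impact trial only. A separate costing plan may exist, so silence is not a decision to ignore sampling error. That stands: the documents support saying that the propagation is not planned in them, and no more. It does not remove the gap, because neither document cites such a plan.

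The 4.55-fold figure is also not a fixed property of the trial. It requires an estimate of 28%, cohort 1 incidence as the denominator and an interval on the log scale. The SE behind it comes from a rounded detectable effect that cannot be checked and that predates the extended study duration in SAP Table 2. This too stands, which is why the size is given as a conditional range.

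A reader might infer that household costs are a minor input and that the plan varies the wrong thing. The documents give no cost figures and no household share of costs, and the societal perspective counts household spending. Varying it is reasonable but incomplete.

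A reader might also infer that the conditional question in section 3.4 biases the ratio downwards. It sets no significance rule, and section 3.6 calculates the ratios unconditionally. The bias arises only if impact is taken to mean a significant result and the ratio is otherwise withheld. Even then it is small at the design effect.

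Finally, cost-effectiveness is a secondary question, and no primary inference is affected. That limits the weight of the point, but the remedy is cheap.

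**Conclusion.** The gap is real. Household-cost variation is the only uncertainty analysis named for the ratio, and the sampling error of its denominator is not carried into it in either document. At the protocol's design effects that error alone spans about 4- to 6-fold. It is unbounded if the observed reduction is about 20% or less, and narrower if the effect is larger (2.7-fold at 35% with the incidence SE). These figures assume costs and the control rate fixed, SEs back-solved from the detectable effects at 80% power and two-sided 5%, and no change in precision from the extended follow-up.

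On the reporting rule, the documents support only that sections 3.4 and 3.6 need reconciling. They do not show that the ratio will be biased. Were it withheld after a non-significant result, it would come out about 5–7% too low at the 28% effect (mean and median), about 24% too low at a true 20% and about 40% too low at a true 15%.

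**What to change.** In protocol section 3.6, with a matching section in the SAP:

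1. Name the cohort and outcome that supply cases prevented, and how they are scaled to the intervention area. Longitudinal prevalence is a share of visits and does not count cases directly. SAP 3.2 calls the cohort 2 and 3 comparisons quasi-experimental.
2. Propagate effect uncertainty jointly with the household-cost range, either by resampling villages within randomisation stratum and arm or by drawing from the fitted effect, and recompute cases prevented and the ratio each time.
3. Report incremental cost and cases prevented, each with a 95% interval. Add an interval for the ratio where it is defined. Where the interval for cases prevented includes zero, show the cost-effectiveness plane or an acceptability curve, because percentiles of the ratio are then not interpretable.
4. Reconcile section 3.4 with section 3.6 by stating that these results are reported whatever the significance of the impact result.

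The cost is some wording and analysis time, with no new data on effects. The downside is a wider and less favourable stated range.

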In 2015, the SLEAC survey conducted in Chad showed that the coverage of SAM care was 37% and was considered moderate (12). The barriers identified by the survey are a strong lack of knowledge about malnutrition and a poor understanding of treatment and the IMCI programs, the barrier of distance and the availability of means to get to health centers.

Analysis of 2018 and 2019 admission data in the outpatient or therapeutic nutritional units of the Guéra shows a high rate of admission of children already known to PECMAS services, specifically children in relapse (after an episode successfully treated) and children readmitted after dropping out of the program (11). This rate decreased significantly between 2018 and 2019, but still exceeds 10% of children admitted in the age groups above 6 months. In addition, exit data show that successful treatment increased significantly between 2018 and 2019, with a significant decrease in the dropout rate from 7.5% to 2.6%. The death rate is quite low, around 0.5%. On the other hand, the occurrence of shortages of RUSF in UNA as reported in the monitoring files (zero stock at the end of the month) over a 2-year period reveals that all the health centers monitored suffered at least one shortage in 2 years. A third of the 18 facilities had shortages observed 5 times or more over the 24 months observed.

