3.2 Study design

We designed a two-arm, cluster-randomized, non-blinded, longitudinal, effectiveness trial to study the impact of the PASIM intervention as compared to the standard of care in the study area. Two study groups will be formed, a control/comparison group, and an intervention group receiving the integrated package of interventions. The activities of the control and intervention group are summarized in Table 1.

Table 1: intervention package in intervention and comparison groups

	Intervention	Comparison
Prevention	Integrated community care group (CCG) Weekly home visits: BCC (pregnancy to 23 mo) Monthly village-level distribution in presence of CCG volunteer of 360 g of soap + 1 L of bleach + 3 kg of CSB++ (non wasted 6-11 mo) MNPs (12-23 mo)	No intervention (some pre-existing CCG with no support since 2019; some areas with punctual preventive interventions)
Screening	Family MUAC (6-23 mo) Integrated CCG (6-23 mo) Weekly home visits: training and supervision of family MUAC, MUAC screening, referral, follow-up on referral through supervisor (NGO promoter)	No intervention (Contact with existing CCG and health system ; some areas with caregivers trained to family MUAC in 2019)
Treatment	Current CMAM protocol (adapted), health center or community site (6-59 mo) SAM/MAM treatment, MUAC only, reduced intensity, culinary demonstrations at community sites Strengthened RUTF/RUSF supply chain Integrated CCG (6-23 mo) Weekly home visits: general and AM specific counselling, ensure RUSF/RUTF compliance Monthly village-level distribution in presence of CCG volunteer of 360 g of soap + 1 L of bleach (6-23 mo)	Same as for intervention group Strengthened RUTF/RUSF supply chain No intervention
Relapse prevention	Integrated CCG Weekly home visits: specific counselling on IYCF (6-23 mo for 6 mo) Monthly village-level distribution in presence of CCG volunteer of 200 g of soap + 400 mL of bleach + 3 kg of CSB++ (6-23 mo for 6 mo)	No intervention

Abbreviation used: BCC, Behavior Change Communication; CCG, Integrated community care group; CMAM, Community-based management of acute malnutrition; CSB++, improved corn-soy-blend for young children; MAM, Moderate wasting; MNPs, Micronutrients powder; MUAC, Mid-upper arm circumference; RUSF, Ready-to-use supplementary food; RUTF, Ready-to-use therapeutic food; SAM, Severe wasting.

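### The cost-effectiveness ratio is labelled societal, but the increment is described only as the cost of added activities, with no control-area cost or between-arm difference in CMAM treatment cost named

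*Protocol*

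**What the plan says.** Protocol section 3.6 opens with the perspective: "Costs will be estimated from a societal perspective, including all costs incurred by institutions and communities". Financial and economic costs are both to be collected. On scope it says: "The analysis will include both the total costs of the program and the incremental costs of additional activities in the intervention area". The ratio is defined in a later sentence: "Incremental cost-effectiveness ratios will be calculated by dividing the incremental costs in the intervention area by the number of cases of acute malnutrition prevented", with the prevented cases counted against the control area. The section then interprets the ratio as the cost of one more favourable outcome in the intervention zone relative to the control zone.

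The named sources are programme documents and expenditure records; for staff, "key informant interviews and focus groups will be conducted with staff involved in program implementation"; and for households, focus groups on the "direct and indirect costs they incur in participating in the program". The section mentions neither control-area costs nor treatment costs added or averted. The SAP has no cost-effectiveness section.

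Treatment itself is delivered in both arms. Protocol 3.5.1 places PASIM on top of the usual national programme (PCIMA in the Protocol, CMAM in the SAP), which the control group also receives. In the treatment row of SAP Table 1 (section 3.2), the comparison column reads "Same as for intervention group" and lists the strengthened supply chain for therapeutic foods in that arm too. On existing uptake, Protocol 3.1.1 reports from a 2015 survey that "the coverage of SAM care was 37% and was considered moderate".

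**The concern.** The denominator of the ratio is an explicit contrast between arms; the numerator is not. CMAM treatment is not an added activity, because both arms have it, but PASIM is meant to change how much of it is used, and in opposing ways. Prevention (behaviour change, CSB++, water treatment) should reduce the number of courses. Family MUAC, monthly screening, referral coupons, tracing of families who did not attend, and adherence visits (Protocol 3.2.3) should increase courses or keep children in treatment. Treatment is free to parents (Protocol 4.4), so much of the resulting cost change falls on institutions, which a societal perspective has to count.

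At stake is the answer to a stated research question on cost-effectiveness (Protocol 3.4), in a project meant to inform national, regional and global policy. An activity-only ratio overstates the cost per case prevented if treatment volume falls, and understates it if treatment volume rises.

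**Working it through.** Section 3.6 states no figure, so there is nothing to reproduce. The check has two parts: what each reading of the text would compute, and whether the sign of the missing term can be known beforehand.

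**1. The readings side by side.** On a common population base, let A be the cost of the added activities, T1 and T0 the CMAM treatment cost in the intervention and control areas, and P the cases prevented.

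- Full between-arm ratio: (A + T1 − T0)/P
- Literal reading (added activities only): A/P. This omits (T1 − T0)/P.
- Generous reading (all costs in the intervention area, nothing subtracted): (A + T1)/P. This charges PASIM with T0/P of treatment that would have happened anyway.

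Neither reading gives the full ratio unless a control-area subtraction is supplied, and section 3.6 does not state one.

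**2. Sign of the omitted term.** Inputs, for illustration only:

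- control coverage c0 = 0.37 (Protocol 3.1.1; SAM, 2015)
- relative fall in wasting incidence r = 0.28 (Protocol 3.5.3; a detectable difference, not a forecast)
- intervention coverage c1: not in the documents, varied
- cost of one course t: not in the documents, left as a symbol

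Change in treated cases per control-arm case = (1 − r)c1 − c0.

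Omitted term per case prevented = t × [(1 − r)c1 − c0]/r.

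Break-even coverage: c1* = c0/(1 − r) = 0.37/0.72 = 0.514.

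| c1 (assumed) | 0.72 × c1 − 0.37 | Courses per 1,000 control cases | Omitted term per case prevented |
|---|---|---|---|
| 37% | 0.2664 − 0.37 = −0.1036 | 104 fewer | −0.37t |
| 45% | 0.3240 − 0.37 = −0.0460 | 46 fewer | −0.16t |
| 60% | 0.4320 − 0.37 = +0.0620 | 62 more | +0.22t |
| 74% | 0.5328 − 0.37 = +0.1628 | 163 more | +0.58t |

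Under the generous reading without subtraction, the overcharge is t × c0/r = 0.37t/0.28 = 1.32t per case prevented.

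**3. Sensitivity to r.** With an assumed r of 10%, break-even falls to 0.37/0.90 = 41%, and the omitted term runs from −0.37t at c1 = 37% to (0.90 × 0.74 − 0.37)/0.10 = +2.96t at c1 = 74%. If coverage does not move, the term is −c0 × t whatever r is.

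**4. Is the sign settled elsewhere?** No. Raising treatment uptake is an aim of the project, but Protocol section 1 reports that in the earlier Mali and Burkina Faso studies more screening did not automatically raise treatment coverage, which stayed below 25%.

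**The case against.** A reader might infer that the plan excludes treatment costs and that the ratio is therefore wrong. The documents do not support that. No sentence excludes them. The commitment to all institutional and community costs could be read to include them. The sentence on added activities lists outputs of the analysis, whereas the sentence defining the ratio refers more loosely to incremental costs in the intervention area and is followed by comparative wording. PASIM also has its own treatment component. This stands: the defect is an undefined numerator in tension with the stated perspective, not a declared omission.

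A reader might also infer that control families' treatment costs will not be collected. That is not stated either. The focus groups are not limited to one arm, the Protocol also uses the word programme for the national treatment programme, and the household and caregiver questionnaires (3.5.5) cover expenditures and use of health services without restriction by arm.

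The illustration has real limits. A 2015 SAM coverage figure is applied to all wasting. Survey coverage is not the same thing as courses per incident case. One unit cost stands for both MAM and SAM. The higher coverage values are assumed. SAP 3.4.3 warns that referrals by the survey teams strongly influence enrolment and treatment coverage in both arms of cohorts 1 and 3, which the calculation ignores. With no treatment cost and no PASIM cost in the documents, it cannot be shown that the conclusion would change. These points rule out a monetary estimate. They do not supply the missing subtraction.

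Finally, cost-effectiveness is a secondary question, asked only if there is an impact. That limits the weight of the point; no primary outcome is affected.

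**Conclusion.** The point holds as a definitional gap that would bias the ratio if section 3.6 were followed as worded. The perspective is called societal, the increment is described as the cost of added activities, and neither a control-area cost nor a between-arm difference in CMAM treatment cost is named. The direction of the bias cannot be known in advance. In the illustration with 37% control coverage and a 28% fall in incidence, it changes sign at about 51% intervention coverage, and the omitted term runs from −0.37 to +0.58 of a course cost per case prevented over assumed coverages of 37% to 74%. These values show that the sign is open; they do not predict its size, and no sum of money can be attached to them. Because cost-effectiveness results are meant to reach planners and funders, the numerator should be defined before any ratio is reported.

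**What to change.** In section 3.6, define incremental cost as total cost in the intervention area (PASIM plus CMAM treatment) minus total cost in the control area (CMAM treatment), per resident child or on another common denominator, with cases prevented expressed on the same base. Take treatment quantities by arm from the cohort 2 registers (admissions, treatment days, inputs given) and multiply by unit costs. Protocol 3.5.3 already has inputs and services copied with a village code for all 100 villages, so assignment to arm is possible.

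Report the activity-only figure as secondary and label it a programme-cost ratio.

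Include household treatment costs for both arms where the planned focus groups allow. Otherwise, state that the treatment component covers institutional costs only. In either case, state that it covers children aged 6-23 months, since cohort 2 is limited to that range while SAP Table 1 lists treatment for 6-59 months.

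The cost is a change of wording in 3.6, the collection of unit treatment costs, and some added costing work. The quantities needed from the registers are already planned for collection.
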